Appendix I: Research Flowchart

[figure not shown]

Appendix II: Timeline of the study:

Work / Months	1	2	3	4	5	6	7	8	9	10	11	12	13	14	15	16	18
Design confirmation stage:																	
- Literature review to validate the protocol, measurements and analysis of the study																	
Preparation stage:																	
- Recruit / train research personnel and recruit Tai Chi instructor																	
- Prepare materials (Tai Chi manual & CD, and stationery) and invitation letter and data collection form																	
Study conduction stage:																	
- Invite centers, recruit and screen participants																	
- Baseline data collection																	
- Conduct the interventions																	
- Outcome assessment and interviews																	
- Data management																	
Project completion stage:																	
- Data analysis																	
- Literature review																	
- Report writing																	
- Dissemination of findings and Manuscript writing																	

Appendix III: Fall management flowchart and guidelines:

*Fall management flowchart during Tai-Chi training lessons (English):

**Follow up :

- 1) All fall accidents will be reported to the research team.
- 2) In all cases, a follow-up phone call will be conducted by the research assistant and will be referred to PI, if any problems.

Guidelines for managing older people who fall while doing Tai-chi / exercise at home (English):

After slipping and falling, elderly people should take the following steps to help themselves:

- 1) Keep calm.
- 2) Assess the level of injury; move slowly if not severe.
- 3) Move along the ground to walls or stable furniture, then climb up with the support of the furniture.
- 4) If you cannot stand up, you may make a call by using the Personal Emergency Link Service / open the main door and ask loud for help.
- 5) Clean the wound first if you get an abrasion.
- 6) Consult a doctor quickly if you note any problems. You may have a fracture if you have difficulty moving or are in severe pain, even without any obvious wound.
- 7) All fall accidents should be reported to the research team.
- 8) In all cases, a follow-up phone call will be conducted by the research assistant and will be referred to PI, if any problems.

*These guidelines have been adopted from Fall prevention. (2011). In Department of Health. Retrieved Feb.12, 2015, from http://www.info.gov.hk/elderly/english/health_tips/eng/falls.htm

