Official Title: The Effects of Simplified 10-step Tai-chi
Programme on the Motor Performance and Fall Prevention of
Community-dwelling Older People With Dementia: a Pilot Cluster
Randomized Control Trial

Date of the document: 16 May 2016

Approved by the Human Subjects Ethics Sub-committee of The
Hong Kong Polytechnic University on 15-Jan-2016

A. Background of Research

Falls in older people are prevalent worldwide. Fall-induced injuries are important health issues in the elderly population and became one of the top leading causes of death in older adults^{10, 11}. Falls are particularly problematic for people with dementia (PWD). Studies have shown that PWD have a significantly higher incidence of falls and also suffered more serious consequences from fractures and hospitalization¹. A meta-analysis of 27 studies reported a strong negative correlation between an increased risk of falling and cognitive functions¹².

Strong evidence exists that falls can be prevented among community-dwelling older people, but there is limited evidence of effective approaches for PWD². In particular, there is a considerable amount of evidence that Tai-chi has beneficial effects on the prevention of falls among older people, including that it reduces their fall rates and fall risks^{13, 14}, enhances their of static balance and flexibility and relieves their fear of falling^{15, 16}.

Tai-chi, a traditional Chinese martial art, is regarded as a body-mind exercise that combines relaxed physical movements and meditation. Although there is considerable evidence that Tai-chi has beneficial effects on physical and mental health in cognitively intact older adults, the underlying mechanisms explaining its effects remain largely unclear. A study conducted in 2014 preliminarily revealed the mechanisms by which Tai-chi improves dynamic postural control in older adults. Tai-chi was shown to increase the centre of pressure (CoP) mediolateral excursions and the resultant CoP centre of mass distance in the medial and forward conditions in the postural phase¹⁷. Older adults who have received training in Tai-chi have higher CoP mediolateral displacement and velocity in the locomotion phase¹⁷ which contribute to better balance and gait performance, leading to a reduction in their fall risks.

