Below is a summary of the strategies that were used in the abovementioned Tai-chi studies, which were considered to support high levels of engagement of PWD in Tai-chi training:

- 1) Involving caregivers as exercise partners so as to provide support and assistance.
- 2) Accommodating the preferences of individuals, and taking particular account of their current abilities when designing the Tai-chi steps. The steps must be simple to reduce the demands on their cognition. Studies have shown that simplified, short forms of Tai-chi that are based on movement improve the balance of older people and reduce their risk of falling in samples without dementia²⁶,²⁷. Thus, simplified instead of traditional Tai-chi steps should be used among PWD.
- 3) Employing special teaching methods to deal with cognitive impairment – such as teaching one step at a time and gradually adding new steps in later sessions according to the participants' progress, using both visual and verbal cues during the instruction, introducing simple Tai-chi steps and using additional tools such as photographs and clear booklets that enable the participants to record their progress and help them to adhere to the exercise regime²⁵.
- 4) Adopting positive emotional motivation techniques to enhance enjoyment of the Tai-chi programme – besides receiving verbal encouragement from the Tai-chi instructors and their caregivers, the participants should also be given an incentive or reward according to their own preferences before or after the Tai-chi practice. These strategies have been shown the effectiveness in enhancing PWD's adherence to the Tai-chi training^{8,9}.

Tai-chi has many known benefits for reducing the risk of falls. However, clinical trials with Tai-chi interventions have tended to exclude PWD, who may be at a high risk of falling but have difficulty participating in formal fall prevention programmes. After tailor-made strategies for PWD were incorporated in Tai-chi training programmes, some preliminary positive effects were noted in several studies, in terms of the feasibility and acceptability of the programmes and their impact on the functional mobility of PWD. However more studies are still required to verify the appropriate strategies for engaging PWD in Tai-chi fall prevention programmes so as to be able to make evidence-based recommendations on reducing fall rates in PWD.

B. Research plan and methodology (Appendix 1: Research flowchart)

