Aim: The aims of this study are to determine the feasibility and acceptability of the simplified 10-step Tai-chi programme for PWD, and to explore the preliminary effects of this intervention on the motor performance of PWD.

Design: A single-blinded cluster RCT will be used to compare the experimental and the control groups. An independent, trained research assistant (RA-assessor) who is blinded to the group assignment will perform the outcome assessments and data entries. A descriptive, qualitative design with focus groups or individual interviews will be used to evaluate the process of implementing the intervention from the perspectives of the participants, their caregivers, and the Tai-chi instructor.

Setting and Sampling: Four community health centres which provide services to PWD will be invited by a convenience sampling method to participate in the study. We will only recruit those community health centres that are funded by the Hong Kong (HK) government and that are under the supervision of Social Welfare Department, which meet a specific set of standardized regulations and criteria on practices, and which provide similar sets of care services for community-dwelling older people. The study's target population is community-dwelling older people with mild to moderate dementia.

The inclusion criteria for participants are: 1) community-dwelling older people of either gender; 2) who are able to communicate in Cantonese to ensure that they understand our instructions during the training, 3) who are able to walk independently with no walking aid or no more than a single point stick for at least 10 minutes so as to ensure their mobility is good enough to allow them

to take part in the Tai-chi training. 4) They must also have received a formal diagnosis of any form of dementia. Their level of cognitive impairment will be assessed using an Abbreviated Mental Test (AMT)^{28, 29} with a score ranging between 5 and 8 to indicate mild to moderate cognitive impairment. 5) Finally, they must identify a caregiver who is willing to work as an exercise partner and facilitator for their practice of Tai-chi.

Sample size: Thirty participants will be recruited for each group. A small sample of 30 per group would be sufficient to test the feasibility of a pilot study³⁰. Twenty participants from the experimental group will be randomly selected to join the focus groups after completing the entire programme.

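### The English home-fall list in Appendix III is addressed to the faller, has no step for the required caregiver, and puts the fracture signs after the instructions to move

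*Protocol*

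**What the plan says.** The home guidelines in Appendix III of the protocol, labelled as the English version, begin "After slipping and falling, elderly people should take the following steps to help themselves". Step 2 reads "Assess the level of injury; move slowly if not severe" and step 3 reads "Move along the ground to walls or stable furniture, then climb up with the support of the furniture". Step 4 offers the emergency link service, or calling out from the front door, to someone who cannot stand. Step 5 deals with abrasions. Step 6 advises seeing a doctor promptly about any problem and adds "You may have a fracture if you have difficulty moving or are in severe pain, even without any obvious wound". Step 7 asks, in the passive voice, for falls to be reported to the research team. Step 8 reads "In all cases, a follow-up phone call will be conducted by the research assistant and will be referred to PI, if any problems". A note says the guidelines were adopted from a Department of Health web page.

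The inclusion criteria (Setting and Sampling) require a formal diagnosis of dementia and an Abbreviated Mental Test result "with a score ranging between 5 and 8 to indicate mild to moderate cognitive impairment". They also require each participant to name a caregiver willing to act as exercise partner. The Background lists, among the strategies of earlier Tai-chi programmes for people with dementia (PWD), "Involving caregivers as exercise partners so as to provide support and assistance". It also states that "PWD have a significantly higher incidence of falls and also suffered more serious consequences from fractures and hospitalization". The SAP says nothing on this subject.

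**The concern.** The list reads as general advice to an older person who has fallen alone. The trial population differs from that in two ways that bear on it. The faller has mild to moderate cognitive impairment, so is poorly placed to judge an injury and recall an ordered list. And the design has already secured a second person, the caregiver, for every participant.

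The order of the steps adds to the difficulty. The decision whether to move is taken at step 2, but the information needed to take it safely (trouble moving, or severe pain without a visible wound) appears four steps later. Someone who works down the page in order has been told how to get up before being told what a fracture may feel like.

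What is at stake is the first few minutes after a fall in the Tai-chi arm's home practice: how bad the injury is, whether the person should be moved, and whether to get help. The protocol's own statement about the consequences of fractures in this population makes those minutes worth a clearer page. No estimate, test or outcome definition depends on it.

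**Working it through.** No arithmetic applies and the plan gives no figure to reproduce. The check is a reading of the eight steps against every other mention of the caregiver.

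**The home list, step by step**

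| Step | Content | Who acts |
|---|---|---|
| 1 | Stay calm | Faller |
| 2 | Assess the injury; move slowly unless severe | Faller |
| 3 | Move to a wall or furniture and climb up | Faller |
| 4 | If unable to stand, use the emergency link or call out | Faller |
| 5 | Clean an abrasion | Faller |
| 6 | See a doctor if there are problems; fracture signs given | Faller |
| 7 | Report the fall | Not stated |
| 8 | Follow-up telephone call | Research assistant, then the principal investigator |

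Six of the eight steps are put to the faller and none names a caregiver, partner or relative. The fracture signs are at step 6; moving and climbing are at steps 2 and 3. Step 4 is the only step that summons help on the spot. It is triggered by being unable to stand, not by suspected serious injury. No step says outright that the person should stay still.

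**What the rest of the protocol gives the caregiver**

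- The Interventions: attends the training sessions with the participant.
- Instruments and Measures: completes the exercise diary, which is backed by weekly calls, and helps record falls in the monthly calendar.
- Intervention fidelity and RA training: two workshops before the programme, with contents still to be developed and no mention of how to respond to a fall.
- Ethical Consideration: risks are explained to participants and caregivers, and the physiotherapist or principal investigator gives advice as needed. For fall management this section points back to Appendix III.

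None of these gives the caregiver a task at the moment of a fall. The diary, calendar, adverse-event record and calls all act afterwards. The flowchart in Appendix III, not reproduced in the text available, concerns falls in training lessons and so does not bear on falls at home.

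**Reading the two together.** The inclusion criteria make a caregiver partner universal, and the Background gives support and assistance as the reason earlier programmes involved caregivers. The home list is the one place where the protocol sets out what to do after a fall during home practice, and it does not call on that person.

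**The case against.** The strongest reply is that the content needed is largely on the page. Step 2 puts assessment first and makes movement conditional, step 4 covers getting help, and step 6 gives the fracture signs. A caregiver who is present can read and apply all of it. The heading, which speaks of managing an older person after a fall, could be taken to address a helper, and the passive wording of step 7 lets a caregiver report. The list comes from a health-department source, and a self-help list is the right form for a fall when nobody else is there. Pairing with the caregiver is required in the training sessions; the protocol does not say that the caregiver attends each home session.

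Much of this stands and sets the limits of the point. What it does not answer is the addressee (the opening line settles that the steps are for the faller), the position of the fracture signs, and the lack of an explicit instruction not to move.

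A reader might go further and infer three things that the documents do not support:

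- That a caregiver present at a home fall has no written instruction. The workshop contents are not given, and participants must speak Cantonese, so the version used at home may be one that is not in the documents.
- That the list tells an injured person to move regardless. Step 2 restricts movement to injuries that are not severe.
- That falls would be missed or the results affected. Falls are recorded through the calendar and the adverse-event record, with reminder and verification calls.

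**Conclusion.** The point holds as a minor, optional participant-safety improvement, confined to the English wording of the home list. The list is addressed to a person with dementia, leaves the judgement of severity to that person, gives the fracture signs after the movement steps, and contains no step for the caregiver whom every participant must have.

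Its size cannot be put as a number of events. That would need the rate of falls during home practice and the share of them with a caregiver present, and the documents give neither. A count of planned home sessions would measure exposure, not risk, so none is offered.

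The conclusion assumes that the unseen material (workshop contents and any Chinese version) does not already supply caregiver steps. If it does, the English page need only be brought into line.

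**What to change.** Reword the home list in this order:

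1. Put the fracture signs from step 6 ahead of any instruction to move.
2. Add steps for a caregiver who is present: check for those signs; do not move the person if a serious injury is suspected; get help; report the fall to the research team.
3. Keep the present self-help steps as a fallback for when the participant is alone.

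Ask the physiotherapist already available to the study to agree the wording, make the same change in any Chinese version, and go through the page in the two planned caregiver workshops.

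The cost is one page reworded, a few minutes of workshop time and notification of the ethics committee. The caregiver's presence should not become a condition of home practice. Practice hours, assessments, outcomes and analysis are unchanged.

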Official Title: The Effects of Simplified 10-step Tai-chi Programme
on the Motor Performance and Fall Prevention of Community-
dwelling Older People With Dementia: a Pilot Cluster Randomized
Control Trial

Date of the document: 16 May 2016

**The effects of a simplified 10-step Tai-chi programme on the motor performance and fall prevention of community-dwelling older people with dementia (PWD):
A pilot cluster RCT study**

Statistical Analysis

SPSS will be used for data analysis. Descriptive statistics will be generated for the demographic data. Normality assumptions for the variables will be checked. The paired t-test or Wilcoxon's signed rank test will be used to examine any significant difference in outcome measurements in the experimental group before and after the implementation of the combined intervention. Student's T-test or the Mann-Whitney U test will be used to examine any significant differences between the control and experimental groups in terms of the outcome variables. For categorical and dichotomous outcome variables, a χ^2 test will be used to identify any significant differences between the groups. A p-value < 0.05 will be considered statistically significant. Mixed effect modelling (MEM) will be further used to measure changes in the outcome measures after intervention with respect to its baseline, and to see the effectiveness of the intervention. Multiple imputations will be adopted to manage missing data.

All interviews will be transcribed and analyzed by content analysis so as to understand participants', caregivers' and the Tai-chi instructor's opinions about the intervention. Coding will occur independently by two members of the research team. Differences in coding between the independent coders will be resolved through discussion between the coders

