Sample recruitment procedures: The centres will be randomized into the control or the Tai-chi groups by using computer-generated random numbers for each of the four centres generated by an independent statistician. We will publicize/promote this study by displaying posters in the centres and asking the centre-in-charges to encourage and refer the eligible subjects to participate. A leaflet containing information about the study and an invitation letter with a reply slip for the participants to indicate their interest in participating in the study will also be mailed to all potential subjects to invite them to participate in this study. A convenience sampling method will be used to recruit participants in the community health centres.

The Interventions

The experimental condition: A 16-week 10-step simplified Tai-chi group training programme will be arranged for the Tai-chi group. During the intervention period, the participants in the Tai-chi group will receive two 1-hour centre-based Tai-chi group training sessions every week.

The participants will be required to pair up with their caregiver to take part in the training sessions together. They will be encouraged to practice the Tai-chi exercises at home for 30 minutes for at least three times per week. Adding up all of the group sessions and the time spent practising at home, each participant should have undergone at least 56 hours of Tai-chi practice during the intervention period. A high dose of 50 hours of exercise practice has been shown to be more effective in reducing fall rates than exercise interventions that require less than 50 hours of practice³¹. A maximum of 7-8 pairs of participants and their caregivers will be supervised by a qualified Tai-chi instructor during each training session. To encourage the participants to practise the Tai-chi exercises at home, a compact disc and a pamphlet describing the 10-step Tai-chi programme will be distributed.

The control condition: As no active fall prevention treatments have been employed among local older people with dementia, the control group will only take part in group recreational activities organized by the district centres. The number and timing of the activities will be similar to those organized in the Tai-chi training session for the experimental group. The participants in the control group will be also instructed to continue their usual lifestyles and levels of physical activity.

Instruments and Measures

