- Dynamic single leg standing balance will be assessed by the Step Test (ST) test³⁸. Participants will stand with their feet parallel and apart for about 10 cm. A block / step with 7.5 cm height will be placed 5 cm in front of the participants. They will be instructed to place the whole foot onto the block, then return it fully back down to the floor repeatedly as fast as possible for 15 seconds. Each leg will be tested separately, and performance on the left or right side with the least number of steps will be the result.

The number of falls will be also recorded by the caregivers and the participants in a monthly falls calendar, in which they will note down any fall accidents that have happened to the participant during the 16-week study period. Monthly phone calls will be made by an RA-observer to remind the participants to return the calendar as well as to verify the records. A fall will be defined as “an unexpected event in which participants come to rest on the floor or lower level⁴¹.” This will be used to guide the participants (caregivers) in recording their fall accidents. The severity of the injuries will also be recorded.

Procedures (randomization, allocation concealment, blinding)

After ethical approval has been obtained, all potential participants will be screened for their eligibility to participate in the study. The participants and their caregivers will then be interviewed to obtain their proxy informed consent, socio-demographic data, and baseline assessment. After that, the four community centres will be randomized to the control or the experimental groups. The participants from each centre will be placed into their centre’s corresponding group to avoid ‘contaminating’ other participants. The changes in the above mentioned preliminary outcome scores from the baseline to interim assessment at Week 8 (T1:Mid-term of intervention) and intervention effects at immediate (T2) after completion of the 16-week interventions will be compared between the groups by the RA-observer.

Twenty participants from the Tai-chi group will be randomly selected to join the focus groups within two weeks after completing the entire programme. Each focus group will contain between 5 and 10 people. The Tai-chi instructor will also be interviewed individually. All interviews will be conducted by the PI in the community health centres to collect the opinions on the design of the intervention. (Appendix II: Timeline of the study)

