All workshops and Tai-chi sessions must follow the protocols and will be run by the same RA/Tai-chi instructor to ensure intervention consistency. Intervention fidelity checking will be conducted in the training period and then monthly to bimonthly during the intervention period based on the workshop/ Tai-chi checklists. Achieving a fidelity rate of >90% will be considered acceptable, based on the recommendations of the NIH Behaviour Change Consortium⁴². This is to ensure that all of the interventions are executed by the Tai-chi instructor or the RA as intended. Monthly to bi-monthly quality-control meetings with all research personnel (the Tai-chi instructor and the RA) will be arranged to evaluate their instruction / facilitation skills in this study.

Statistical Analysis

SPSS will be used for data analysis. Descriptive statistics will be generated for the demographic data. Normality assumptions for the variables will be checked. The paired t-test or Wilcoxon's signed rank test will be used to examine any significant difference in outcome measurements in the experimental group before and after the implementation of the combined intervention. Student's T-test or the Mann-Whitney U test will be used to examine any significant differences between the control and experimental groups in terms of the outcome variables. For categorical and dichotomous outcome variables, a χ^2 test will be used to identify any significant differences between the groups. A p-value < 0.05 will be considered statistically significant. Mixed effect modelling (MEM) will be further used to measure changes in the outcome measures after intervention with respect to its baseline, and to see the effectiveness of the intervention. Multiple imputations will be adopted to manage missing data.

All interviews will be transcribed and analyzed by content analysis so as to understand participants', caregivers' and the Tai-chi instructor's opinions about the intervention. ???Coding will occur independently by two members of the research team. Differences in coding between the independent coders will be resolved through discussion between the coders.

Ethical Consideration

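### A p<0.05 before/after test in the Tai-chi arm alone is not ranked below the between-group comparison that the trial is designed to make

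*SAP*

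**What the plan says.** The SAP's Statistical Analysis section lists its tests in this order.

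- **Within one arm.** A paired t-test or Wilcoxon "signed rank test will be used to examine any significant difference in outcome measurements in the experimental group before and after the implementation". The protocol's Statistical Analysis section has the same text, restricting the test to change "in the experimental group before and after the implementation of the combined intervention". Neither document plans a matching test in the control arm.
- **Between arms.** A t-test or Mann-Whitney test "will be used to examine any significant differences between the control and experimental groups in terms of the outcome variables". The wording does not say whether this uses follow-up scores or changes, and it names no baseline term.
- **Threshold.** One p<0.05 rule, with no exception for the one-arm test.
- **Mixed model.** Used in addition, "to measure changes in the outcome measures after intervention with respect to its baseline, and to see the effectiveness of the intervention". No terms are listed: no group-by-time contrast and no centre effect.

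Elsewhere the protocol makes the question comparative. Under Design, the cluster trial "will be used to compare the experimental and the control groups". Under Procedures, "intervention effects at immediate (T2) after completion of the 16-week interventions will be compared between the groups". Under The control condition, the recreational sessions are matched: "The number and timing of the activities will be similar to those organized in the Tai-chi training session for the experimental group". Under Aim, the efficacy part is exploratory: "to explore the preliminary effects of this intervention on the motor performance of PWD".

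Neither document names a primary effect analysis or calls the one-arm test descriptive or supportive.

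**The concern.** The control arm, with sessions matched in number and timing, is there to show what happens without Tai-chi. The before/after test in the Tai-chi arm does not use it. Participants repeat the motor tests at baseline, Week 8 and the end of the 16 weeks, so scores may move through familiarity with the tests, attention or the passage of time. The one-arm test counts all such movement together with any Tai-chi effect.

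The error can go either way. If both arms improve alike, the test can look like evidence of benefit. If both arms decline alike, it can hide a real benefit.

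Because the tests are not ranked, a significant one-arm result could stand beside a non-significant between-arm result with no written statement of which is the trial's estimate of effect. The protocol refers to a future main study, so a misread preliminary effect could carry forward.

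**Working it through.** **Inputs from the documents.** 30 participants per group (Protocol, Sample size); p<0.05, taken as two-sided because sidedness is not stated (Statistical Analysis); four centres (Protocol, Procedures).

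**Assumptions.** The documents give no SD, shift, correlation or intracluster correlation (ICC). I assume no Tai-chi effect, the same mean shift s in both arms (in SDs of the outcome, equal at both times), a correlation r of 0.7 or 0.8 between baseline and follow-up, all 30 analysed, and clustering ignored. The plan states no power figure for these tests, so there is none to reproduce first.

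**Step 1: standardise the change.** The SD of a change score is √(2(1−r)), which is √0.6 = 0.775 at r = 0.7 and √0.4 = 0.632 at r = 0.8. So d_z = s/√(2(1−r)), and the non-centrality of the paired t-test is d_z·√30.

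**Step 2: chance that the one-arm test is significant** (non-central t, 29 df, critical value 2.045).

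| Shared shift s | d_z (r = 0.7 / 0.8) | Non-centrality | Significant |
|---|---|---|---|
| 0 | 0 / 0 | 0 / 0 | 5.0% / 5.0% |
| 0.1 SD | 0.129 / 0.158 | 0.707 / 0.866 | 10.5% / 13.3% |
| 0.2 SD | 0.258 / 0.316 | 1.414 / 1.732 | 27.7% / 38.8% |
| 0.3 SD | 0.387 / 0.474 | 2.121 / 2.598 | 53.6% / 70.9% |

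These rates are per outcome. The test is two-sided, but at 0.2 SD and above almost every rejection is in the direction of the shift.

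**Step 3: the between-arm test on changes.** The expected difference is s − s = 0 whatever the shift. Simulation without clustering (40,000 trials per setting) gives rejection in about 5% throughout.

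**Step 4: a shared decline.** A true benefit of 0.2 SD with a shared decline of 0.2 SD gives a net change in the Tai-chi arm of 0.2 − 0.2 = 0. The one-arm test then rejects at its 5% null rate although the benefit is real.

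**Step 5: is clustering part of this defect?** Assume 2 centres per arm, 15 participants each, zero shift, no effect, and ICC defined on the baseline-adjusted residual. The one-arm test rejects in about 12-13% of trials at ICC 0.05 and 19-20% at ICC 0.10. An ordinary between-group t-test on changes that ignores centre rejects at about the same rates (12-13% and 19-20%). This inflation comes from ignoring centre, not from testing one arm.

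**The case against.** The strongest reply is that the documents already separate the roles. The one-arm test has the narrow task of looking for change within the Tai-chi group, only the mixed model is linked to effectiveness, and Design and Procedures both speak of comparing groups. Nowhere is the before/after p-value said to show efficacy. This is a pilot whose first aims are feasibility and acceptability, so harm requires a later author to misread the result.

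Much of that stands, and it limits the severity. A reader might infer that the plan has no between-group analysis, or that it will claim efficacy from the one-arm test; the text supports neither. The link to effectiveness is still not a ranking, because the model is an addition to the other tests, its between-arm contrast is unnamed, and the p<0.05 rule treats all tests alike. The exploratory label covers every effect analysis and does not order them.

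Three other stronger readings also fail.

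- **The one-arm test is to blame for rejection rates of 12% and 19% with no shift at all.** Step 5 shows that a between-group test ignoring centre shares these rates.
- **The one-arm test will contradict the proper analysis in 34-42% of null trials** (0.2 SD shared shift, ICC 0.10). That figure takes as comparator a centre-level test on 2 df, which the plan does not contain, and partly reflects that test's low power. Against a t-test on changes the figure is about 27-34%.
- **The mixed model leaves out centre.** The documents list no terms, so centre is unspecified, not shown to be excluded.

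**Conclusion.** The concern holds in a limited form. Both documents plan a significance test in the Tai-chi arm alone and do not rank it below the comparison that the design exists to make. With no Tai-chi effect, its chance of significance per outcome rises from 5% to about 28-39% at a shared shift of 0.2 SD; the full range is in Step 2. These figures rest on assumed shifts and correlations and ignore clustering. They show how the test behaves and do not forecast this trial.

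No decision rule uses the p-value and the motor outcomes are exploratory, so the consequence is a possible misreading of preliminary effects, not a wrong formal decision. Severity is minor to moderate. Confidence is high about what the documents say and lower about how likely the misreading is.

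**What to change.** Change the Statistical Analysis section in both the SAP and the protocol, since they carry the same text.

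1. Remove the paired t/Wilcoxon test as inference. Show mean change with its confidence interval, descriptively, in both arms.
2. Name one effect estimate: the between-arm difference at T2 (and at T1) from the mixed model already planned, adjusted for the participant's own baseline score, accounting for centre, with a degrees-of-freedom method suited to few clusters, reported with its 95% confidence interval.
3. State that the unadjusted t/Mann-Whitney results rank below that estimate.
4. If a centre-level analysis is also wanted (2 df, assuming two centres per arm), label it a sensitivity analysis, not an alternative main estimate.

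**Cost.** Wording only; baseline is already collected in everyone. The change improves validity, not power. Under the assumptions above, the 2-df form has about 16-21% power for a 0.3 SD benefit at ICC 0 and 10-12% at ICC 0.10 (ICC on the baseline-adjusted residual). Its mean 95% half-width is about 0.6-0.7 SD and 0.9-1.1 SD respectively. The motor results should therefore be reported as exploratory estimates, in line with the stated aim.
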